3.2.3.6 Vital Signs Changes

Vital signs include blood pressure (systolic and diastolic), pulse rate, body temperature, respiration rate, body weight and BMI. Body height is assessed only at screening and is part of baseline characteristics only. BMI over time will be derived based on baseline body height. Vital signs data obtained up until the end of treatment visit will be used for reporting.

Change from baseline in vital signs variables will be calculated for each post-dose visit, see section 3.1.2. End of treatment results will be those which are assessed on the latest nominal visit prior or on the date subjects discontinue or complete study intervention.

3.2.3.7 ECG Changes

The QTcF will be derived during creation of the reporting database using the reported ECG values (RR and QT):

$$QTcF = QT/(RR(1/3)), \text{ where RR is in seconds.}$$

For numeric ECG parameters, triplicate ECG assessments will be programmatically derived using the averaged by time point and change from baseline will be calculated for each post-dose visit, see section 3.1.2. End of treatment results will be those which are assessed on the latest nominal visit prior or on the date subjects discontinue or complete study intervention.

The Bazett's Correction Formula (QTcB) may also be derived if it is the local standard.

3.2.4 CCI

CCI

3.2.4.1 Change in tumor size

Tumor size is the sum of the longest diameters (or short axis measurements for lymph nodes) of the target lesions. Target lesions are measurable tumor lesions. Baseline for RECIST is defined to be the last evaluable assessment within 28 days prior to first administration of study intervention. The percentage change in target lesion tumor size at each week [CC1] until [CC1] and [CC1] onwards) for which data are available will be obtained for each subject taking the difference between the sum of the target lesions at each week [C] and the sum of the target lesions at baseline divided by the sum of the target lesions at baseline multiplied by 100 (i.e. (week [CC1] - baseline)/baseline * 100).

The tumor size and percentage change from baseline in the sum of tumour size at each assessment will be calculated. The best change in tumor size from baseline (i.e. depth of response) is the largest decrease from baseline or the smallest increase from baseline in the absence of a reduction and will include all assessments prior to the earliest of death in the absence of progression, any evidence of progression, the start of subsequent anti-cancer therapy or the last evaluable RECIST assessment is the subject has not died, progressed or started subsequent anti-cancer therapy.

No imputation methods will be considered for missing data in tumor size.

4 ANALYSIS METHODS

The analysis for the study will be descriptive only. There will be no formal statistical hypotheses.

4.1 General principles

The below mentioned general principles will be followed throughout the study:

- Descriptive statistics will be used for all variables, as appropriate. Continuous variables will be summarized by the number of observations, mean, standard deviation, median, upper and lower quartiles (as applicable), minimum, and maximum. For log transformed data (in this study only applicable to PK concentrations) it is more appropriate to present geometric mean, coefficient of variation (CV), median, minimum and maximum. Categorical variables will be summarized by frequency counts and percentages for each category.
- By visit, data will be presented until at least 3 subjects have evaluable data. A minimum of 12 cycles will be presented in any case. If data are available for less than 3 subjects within the first 12 cycles, no summary statistics other than minimum, maximum and number of observations will be presented.
- Unless otherwise stated, percentages will be calculated out of the analysis set total.
- For continuous data the mean and median (1st quartile and 3rd quartile, if present) will be rounded to 1 additional decimal place compared to the original data. The standard deviation will be rounded to 2 additional decimal places compared to the original data. Minimum and maximum will be displayed with the same accuracy as the original data.
- For categorical data, percentages will be rounded to 1 decimal place.
- SAS® version 9.4 or higher will be used for all analyses.
- For assessments on the day of first dose where time is not captured, a nominal pre-dose indicator, if available, will serve as sufficient evidence that the assessment occurred prior to first dose. Assessments on the day of the first dose where neither time nor a nominal pre-dose indicator are

captured will be considered prior to the first dose if such procedures are required by the protocol to be conducted before the first dose.

- It is acceptable to present large numerical values in more appropriate units. For example, an AUC value of 123,000 ng·h/mL may be reported as 123 µg·h/mL instead of 123,000 ng·h/mL. It is, however, important to keep the units consistent within the report and the precision consistent with that prior to conversion.

4.2 Description of analysis methods

In general, summaries will be presented by study phase ('Induction Phase', 'Maintenance Phase', 'Overall'), if applicable, and treatment population ('Total', 'SoC', 'AZD2811 + Durva'). The summaries for 'SoC' present results for subjects who withdrew the treatment during induction phase or continued in maintenance with durvalumab monotherapy, whereas 'AZD2811 + Durva' summarizes results for subjects who entered maintenance phase and have been dosed with AZD2811 and durvalumab in maintenance phase. Note that per CSP v8.0 patients in 'AZD2811 + Durva' are planned to be summarized by starting dose of AZD2811, however it should be noted that all patients received the same starting dose and therefore will be summarized together as a single group. In presentations by study phase, the combination of 'Induction Phase' and 'AZD2811 + Durva' is presenting results assessed in induction phase for subjects who entered maintenance phase. The subjects included in 'SoC' who withdrew during induction will be excluded from maintenance phase.

Listings will be sorted by group ('AZD2811 + Durva' first, followed by 'SoC'), if applicable, and by subject. If there are subjects who are assigned to treatment, but didn't receive any study intervention, they will be presented at the end of the listings with missing group.

The full list of planned outputs is provided in Appendix A.

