9.4.1 General Considerations

The main aims of the study are to assess the efficacy, safety, and tolerability of the study intervention in participants who entered the maintenance phase with ES-SCLC.

All analyses will be descriptive, including summaries from Kaplan-Meier curves. Continuous variables will be summarized by the number of observations, mean, standard deviation, median, upper and lower quartiles (as applicable), minimum, and maximum. Log-transformed

data will include geometric mean, geometric standard deviation, and coefficient of variation (CV). Categorical variables will be summarized by frequency counts and percentages for each category. Unless otherwise stated, percentages will be calculated out of the population total for the relevant analysis.

The summaries, where applicable, will be presented by the following: All participants, participants who only entered the induction phase, and participants who entered the induction and maintenance phase, unless otherwise specified.

From CSP v8.0 onwards, the starting dose of AZD2811 in the maintenance phase was intended to be ~~CC1~~ [REDACTED], and the study would therefore report efficacy and safety by maintenance phase starting dose of AZD2811 as applicable. Due to early termination of enrolment, CSPv8 was never implemented and no new pts started treatment with AZD2811; all new patients transitioning into the maintenance phase were treated with durvalumab monotherapy. Further details will be provided in the SAP.

Baseline will be the last non-missing value obtained prior to the first dose/administration of study intervention in the induction phase, and any information taken after first dose/administration of study intervention in the induction phase is regarded as post-baseline information. All analyses will use this baseline unless otherwise specified.

An exploratory analysis using external control data will be conducted to compare AZD2811 + durvalumab to durvalumab from the CASPIAN study and will be reported outside of the CSR.

Induction Phase

The induction phase will be from the first dose of platinum-based induction therapy (cisplatin or carboplatin plus etoposide) + durvalumab until the first dose of AZD2811 + durvalumab in the maintenance phase.

Maintenance Phase

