If a subject does not discontinue, does not withdraw consent, does not progress during the induction phase (tumor assessment at week 6 or with symptomatic PD) or does not die in the induction phase, subjects will be assessed for disease progression in week **[REDACTED]** which is used to confirm eligibility for maintenance therapy. Subjects who either progress or are not eligible for maintenance for other reasons will have the end date of induction phase at the date of the respective Response Evaluation Criteria in Solid Tumors (RECIST) v1.1 assessment. These subjects roll over into safety follow-up period.

Subjects who do not progress based on RECIST v1.1 or die, and are assessed to be eligible to continue into maintenance phase are considered to have the induction phase completed with end date one day before date of first study intervention in maintenance phase.

Maintenance period

Participants who have not progressed per RECIST v1.1 at the end of the induction phase and who meet maintenance phase eligibility criteria will continue into the maintenance phase of the trial and be treated with AZD2811 + durvalumab or durvalumab monotherapy as maintenance therapy. The maintenance phase starts when a subject receives the first administration of IP (AZD2811+durvalumab or durvalumab monotherapy) in the maintenance phase.

Assessments performed pre-dose on CCI [REDACTED] will be considered part of the induction phase unless based on the time collected indicates that the assessment occurred after the first dose in the maintenance phase. Assessments performed on day of dosing where time is not collected are assumed to have been done pre-dose. Maintenance phase end date is the date of end of last treatment during maintenance phase (maximum of end of treatment of AZD2811 and end of treatment of durvalumab). Subjects can discontinue from maintenance phase by withdrawal of consent, progression, death or if other discontinuation criteria are met. A subject who has been treated for a minimum of 2 years of maintenance treatment and continues to experience CR, PR, or SD, as demonstrated by radiographic measures, may be considered for treatment discontinuation.

Safety and survival follow-up period

Safety (concomitant medications and AEs/serious adverse events) will be followed up until 90 days after last dose. Start date of safety follow-up period is one day after end of treatment date in either induction or maintenance phase as per eCRF. The end date is

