4.2.3.2 Adverse events

Data from all cycles (of induction and maintenance phase) will be presented separately as well as combined.

The majority of the AE summaries, unless stated otherwise, will be based on TEAEs. See section 3.2.3.3 for definition of treatment emergence. Any AE occurring within the defined 90-day follow-up period after discontinuation of study intervention will be included in the AE summaries. Any AEs in this period that occur after a subject has received further therapy for cancer (following discontinuation of study intervention) will be flagged in the data listings and will be excluded from above summaries. Numbers and percentages of subjects will be presented for all AEs, AEs with grade ≥ 3 , AEs grade 5, possibly related AEs, possibly related AEs with grade ≥ 3 , possibly related AEs with grade 5, serious AEs and possibly related serious AEs.

AEs occurring prior to first dose of investigational product (i.e. before study Day 1), or after the 90-day follow-up period after discontinuation of investigational product will be listed.

An overall summary table of the number of subjects experiencing each category of AE will be produced. Following categories will be included:

- Any AE
- Any AE of CTCAE grade 3 or higher
- Any AE with outcome = death
- Any SAE (including events with outcome = death)
- Any SAE leading to discontinuation of treatment
- Any AE leading to discontinuation of treatment
- Any AE leading to reduction of treatment
- Any AE leading to dose interruption of treatment
- Any AE leading to modification of treatment (either an interruption and/or a dose reduction)
- Any AESI or AEPI

Except for any AE leading to reduction, dose interruption or modification of treatment and any other significant AE, all categories will be duplicated as applicable to add the condition of being possibly related to treatment (overall and separately for etoposide or cisplatin/carboplatin, etoposide or cisplatin/carboplatin or durvalumab, durvalumab, AZD2811, durvalumab or AZD2811).

Besides the overall summary table, following presentations of number of subjects experiencing TEAEs and of number of AEs will be presented:

- Number of subjects with AEs by SOC and PT
- Number of AEs by SOC and PT
- Number of subjects with AEs, most common (frequency of $>10\%$) by PT
- Number of subjects with AEs by SOC, PT and maximum reported CTCAE grade
- Number of subjects with AEs of CTCAE grade 3 or higher by SOC and PT

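### SAP 4.2 pools induction-only subjects with durvalumab-monotherapy maintenance subjects as 'SoC', so the Induction, Overall and unsplit safety columns set a selected AZD2811 group beside one holding all induction failures

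*SAP*

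**What the plan says.** Protocol 9.4.1 planned summaries for three groups: "All participants, participants who only entered the induction phase, and participants who entered the induction and maintenance phase". The wording allows the SAP to specify otherwise.

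SAP 4.2 crosses three phases (Induction, Maintenance, Overall) with three populations (Total, 'SoC', 'AZD2811 + Durva'). 'SoC' is "subjects who withdrew the treatment during induction phase or continued in maintenance with durvalumab monotherapy". 'AZD2811 + Durva' is "subjects who entered maintenance phase and have been dosed with AZD2811 and durvalumab in maintenance phase". One safeguard follows: "The subjects included in 'SoC' who withdrew during induction will be excluded from maintenance phase". The Induction cell for the AZD2811 population is described in broader terms: it "is presenting results assessed in induction phase for subjects who entered maintenance phase".

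For adverse events, SAP 4.2.3.2 adds: "Data from all cycles (of induction and maintenance phase) will be presented separately as well as combined". The route into maintenance is set in SAP 3.1.3: "Participants who have not progressed per RECIST v1.1 at the end of the induction phase and who meet maintenance phase eligibility criteria will continue" on AZD2811 + durvalumab or on durvalumab alone. SAP Section 6, which lists changes from the protocol, has no entry for the regrouping.

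**The concern.** The two named populations are separated partly by treatment and partly by whether the subject got through induction. A subject who dies, progresses or drops out during induction cannot be in 'AZD2811 + Durva' and so lands in 'SoC'. The safeguard removes such subjects from the Maintenance presentation only.

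The abbreviated CSR exists mainly to report safety in full, on a drug whose development in this setting ended because of its benefit-risk profile. A reader of an Overall table of deaths, discontinuations or grade 3 or higher events will naturally compare the two columns. The heading 'SoC' encourages this, because it looks like a control arm in a study that has none. Part of any difference seen there would reflect who reached maintenance and how long they were observed, not what AZD2811 did.

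**Working it through.** The plan states no figure to reproduce. The check is to trace who falls in each cell and then to ask how large a composition effect could be.

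**Composition of the columns**

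| Subject | Induction / Overall | Maintenance |
|---|---|---|
| Left study treatment during induction | 'SoC' | excluded |
| Progressed or ineligible at the end-of-induction scan | 'SoC' by default | not treated in this phase |
| Durvalumab monotherapy in maintenance | 'SoC' | 'SoC' |
| AZD2811 + durvalumab in maintenance | 'AZD2811 + Durva' | 'AZD2811 + Durva' |

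The second row needs inference. SAP 3.1.3 recognises these subjects and sends them to safety follow-up, but the 'SoC' definition speaks only of withdrawal during induction. The listing rule in SAP 4.2 leaves the group blank only for subjects who received no study intervention, so 'SoC' is where they end up.

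The gate is absence of progression plus maintenance eligibility. It does not require an event-free induction: Protocol 6.1.2 allows entry to maintenance after a chemotherapy agent is stopped for toxicity, following consultation. The AZD2811 column can therefore include induction toxicity, but not induction deaths, progressions or withdrawals from study treatment.

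**Observation window.** SAP 3.1.3 and 3.2.3.4 assign safety follow-up events to the phase the subject left. For an induction dropout, events up to 90 days after the last dose count as Induction. For a subject who goes on to maintenance, Induction ends the day before the first maintenance dose. The Induction columns thus differ in follow-up as well as in selection.

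**Size.** Let f be the number of induction failures and m the number of monotherapy maintenance subjects. Let pf be the event rate in failures and pc the rate in subjects who reach maintenance, with no treatment difference. Then

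'SoC' rate − AZD2811 rate = (f·pf + m·pc)/(f + m) − pc = [f/(f + m)] × (pf − pc).

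Inputs:
- 9 AZD2811 patients (Protocol 9.4).
- Safety-set size N is not given; 20 to 60 is assumed.
- Induction loss is not given. Two planning figures are borrowed: 100 assigned for 80 evaluable gives 1 − 80/100 = 20%; the Protocol 9.2 estimates of 130 assigned and 90 evaluable give 1 − 90/130 = 30.8%. Evaluable there means dosed with AZD2811, so these may overstate loss in induction itself.

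With f = loss × N (rounded) and f + m = N − 9:

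| N | f/(f + m), 20% loss | f/(f + m), 30.8% loss |
|---|---|---|
| 20 | 4/11 = 36.4% | 6/11 = 54.5% |
| 30 | 6/21 = 28.6% | 9/21 = 42.9% |
| 40 | 8/31 = 25.8% | 12/31 = 38.7% |
| 60 | 12/51 = 23.5% | 18/51 = 35.3% |

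The corresponding share in 'AZD2811 + Durva' is 0 of 9 by definition.

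As an illustration, take pc = 50% for grade 3 or higher events in induction. With pf = 70%, the smallest spurious gap is 23.5% × 20 = 4.7 points; with pf = 90%, the largest is 54.5% × 40 = 21.8 points, both making 'SoC' look worse. If failures instead had fewer recorded events, say pf = 30% because they were observed for less time, the gap reverses to between −4.7 and −10.9 points (54.5% × −20). The sign follows pf − pc, which the documents do not determine. These event rates are assumptions.

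In the Overall columns both forces act. Early deaths and discontinuations load 'SoC', while a guaranteed minimum time on study and an added drug raise cumulative percentages for AZD2811. Protocol 9.4.4 foresaw exposure-adjusted rates where appropriate; SAP 4.2.3.2 lists none.

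**The case against.** The strongest reply is that the contrast of most interest is already displayed. AZD2811 is given only in maintenance, and there 'SoC' reduces to the monotherapy group. The two fatal SAEs attributed to AZD2811 in Protocol 4.1.2.2.1 belong to maintenance treatment and would appear in that column. A reader might infer that the pooling hides an excess risk of AZD2811 over durvalumab alone. The documents do not support that: the Maintenance tables isolate the comparison, the direction of distortion elsewhere is mixed, and the group sizes and event counts needed to show masking are not given.

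Further points on that side also stand. All displays are descriptive (SAP Section 4), there is a Total column, and data are listed by subject, so with 9 patients every case can be inspected. Events unequivocally due to progression are not reported as AEs (Protocol 8.3.7), so induction progressions do not by themselves load the AE tables. The protocol's own third group would have merged AZD2811 and monotherapy subjects, so simply restoring it would not give the useful contrast. Allocation between the two maintenance treatments followed the dosing pause and the end of AZD2811 starts, so splitting the column does not make the groups comparable.

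A reader might also see a contradiction in the sentence on the Induction cell. Coming after the column definition in the same paragraph, it is better read as loose shorthand.

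What survives is narrower. None of this removes the selection from the Induction, Overall and unsplit columns, and the latitude in Protocol 9.4.1 to specify otherwise does not explain why Section 6 is silent on a change of grouping when it lists smaller ones.

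**Conclusion.** The point holds as a problem of presentation, confined to the Induction and Overall columns and to tables not split by phase. There, 'AZD2811 + Durva' is conditional on reaching maintenance without progression and 'SoC' is not. This follows from the definitions alone, whatever the group sizes. The numerical effect is the share of failures in 'SoC' times the difference in event rate between failures and subjects who reach maintenance. Under the assumed sizes and losses that share is about 24% to 55%. The resulting gap could be several points or, at the extreme assumption, about 22, and its sign is not fixed.

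It does not invalidate the Maintenance safety tables, and it does not show that risk is concealed. It is a cheap improvement worth making in a report centred on safety, together with an undeclared departure from Protocol 9.4.1 and two wording gaps in SAP 4.2.

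**What to change.** In SAP 4.2 and the affected table shells:

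- In Induction, Overall and unsplit tables, divide 'SoC' into 'Induction only (did not enter maintenance for any reason)' and 'Durvalumab monotherapy maintenance', beside Total and 'AZD2811 + Durva'. The phrase 'for any reason' gives subjects who progressed or were ineligible at the end-of-induction scan a stated place. It also makes clear that they are outside the Maintenance denominator.
- Reword the Induction cell for the AZD2811 column as 'subjects later dosed with AZD2811 + durvalumab'.
- Footnote that both maintenance groups are conditional on getting through induction and were not formed by randomisation.
- Record the regrouping in SAP Section 6 as a change from Protocol 9.4.1.

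The cost is one more column and a few sentences, with no new data. The drawback is small cell counts, which can be shown as counts with percentages read cautiously. The Maintenance tables need no new column.

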4.2.1 Demographic, safety and tolerability data

There is no formal statistical analysis of demographic, safety and tolerability data required for this study and descriptive statistics will be used.

Tables will present number and percentage of subjects for categorical variables and summary statistics for continuous variables (unit in brackets) for following data (analysis population is Safety unless otherwise specified):

- Subject disposition (Enrolled)
- Important protocol deviations, including information on pandemic related important protocol deviations
- Analysis sets (no analysis population)
- Demographic characteristics, including age (years), age group 1 and 2, sex, race, ethnic group and country
- Subject characteristics, including height (cm), weight (kg), weight group, BMI (kg/m²) and BMI group
- Subject recruitment by region, country and center
- Nicotine use and consumption, including substance usage categories and consumption (pack-years)
- Medical history by system organ class and preferred term
- Disease characteristics at baseline, including Eastern Cooperative Oncology Group (ECOG) performance status, primary tumor location, site of metastatic disease, tumor laterality, histology

type, tumor grade, AJCC staging (American Joint Committee on Cancer) and time from original diagnosis to first administration in induction phase (weeks)

- All allowed concomitant medications during study by ATC classification and generic term

Subjects affected by the COVID-19 pandemic will be listed including category for study disruption due to the pandemic and details of the disruption.

All data summarized in tables will be included in listings. Disallowed concomitant medications, prior cancer therapy, post-discontinuation disease-related anticancer therapy, radiotherapies and pregnancy data (pregnancy test results and pregnancy reports) will be listed only.

